9.4 Subject Restrictions

Subjects and their female partners will have to comply with the following restrictions:

- Blood donation will not be allowed at any time during the study and up to 3 months (90 days) after completion of the study
- Male subjects should not donate sperm and their female partners should not donate egg(s) from the time of the first administration of IMP until 3 months after the last administration of IMP
- Condoms, femidoms, diaphragms, caps or hormone rings are not permitted as a form of contraception in this study

9.5 Subject Inclusion and Randomisation

Subjects who sign the ICF for the study at Visit 1 and undergo screening procedures will be identified during screening by a unique screening number. Subjects who fulfil the eligibility criteria will be assigned consecutive subject numbers and randomised before study medication is dispensed on Day 1 of the treatment period (Visit 2).

Subjects will be randomised to receive one of the following gel treatments in a 1:1:1:1 ratio according to a parallel group design (i.e. subjects will receive one treatment only):

- MED2005 0.2% (w/w) GTN gel to deliver a 0.6 mg dose of GTN
- MED2005 0.4% (w/w) GTN gel to deliver a 1.2 mg dose of GTN
- MED2005 0.6% (w/w) GTN gel to deliver a 1.8 mg dose of GTN
- Placebo vehicle

Subjects will be stratified for randomisation based on their baseline ED severity scores from the end of the screening period:

- Mild (IIEF-EF domain score of 17–25)
- Moderate (IIEF-EF domain of 11–16)
- Severe (IIEF-EF domain \leq 10)

It is intended to randomise an approximately equal number of subjects for each baseline severity group. No stratification by site will be done as, with four treatment groups and three baseline ED severity strata, it is not deemed feasible without risking overall balance for treatments.

If a subject discontinues from the study, the subject number will not be re-used and the subject will not be allowed to re-enter the study.

Randomisation will be carried out using an IVRS/IWRS.

For the open-label extension phase, eligible subjects who sign the ICF for the extension phase at Visit 6 will continue in the study. All subjects will receive MED2005 0.6% (w/w) GTN gel to deliver a 1.8 mg dose of GTN.

9.6 Withdrawal of Subjects

Each subject (and their female partners) will be informed of their right to withdraw from the study at any time and for any reason. The reasons for any subject withdrawal will be recorded on the electronic Case Report Form (eCRF).

9.6.1 Criteria for Withdrawal from Study Drug

Subjects (and their female partners) may be withdrawn from the study drug at any time. All subjects who withdraw from the study drug during the double-blind phase will be asked to continue completing the IIEF and SEP questionnaires in order to address the primary efficacy objective of difference between treatment policies.

A PI will withdraw a subject from study drug at any time for any of the following reasons:

- If a subject experiences a serious or intolerable AE, that prevents them from continuing.
- If a subject incurs a significant protocol violation which impacts on their safety (this will be discussed on a case-by-case basis with the Sponsor).
- At the request of the Sponsor.
- If it is considered that the subject's health is compromised by remaining in the study or the subject is not sufficiently cooperative.

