9.6.2 Criteria for Withdrawal from the Study

Subjects (and their female partners) are free to withdraw from the study at any time, without prejudice (withdrawal of consent).

Subjects may be withdrawn from the study at any time; however, once treatment has commenced, every attempt should be made to continue with the safety and IIEF and SEP questionnaires up to the end of the double-blind phase to ensure the safety of the subject and in order to address the primary efficacy objective of difference between treatment policies.

Reasons for withdrawing a subject from the study can include:

- Voluntary discontinuation by the subject and/or his female partner, who are free to discontinue participation in the study at any time
- Severe non-compliance to the protocol as judged by the PI and/or Sponsor
- Any other reason as judged by the PI

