14.1 Analysis Sets

The following analysis sets will be used for the statistical analysis of the double-blind phase:

- The **randomised set** will consist of all subjects who were randomised to a treatment
- The **safety set** will consist of all subjects in the randomised set who made use of the medication at least once. In the case of randomisation/treatment errors, subjects will be analysed according to treatment received

- The **full analysis set** (FAS) will consist of all subjects in the randomised set who made use of the medication at least once. In the case of randomisation/treatment errors, subjects will be analysed according to randomised treatment
Primary and secondary analyses will be performed on the FAS.
- The **per protocol set** (PP) will consist of all subjects in the FAS who completed the 12-week treatment period without major protocol violations and who have valid IIEF, SEP Question 2 and SEP Question 3 assessments at Week 12 (Visit 5)

Analysis sets will be identified prior to the unblinding of the study data. The efficacy analysis will be performed as randomised; i.e. a subject will be assigned to the treatment he was initially allocated, irrespective of what treatment was actually applied, and whether or not treatment was discontinued while questionnaire data was collected (see [Section 9.6](#) Withdrawal of Subjects).

In order to assess the consistency of results, sub-group analyses will also be performed according to three subject baseline ED severity groups:

- Mild (IIEF-EF domain score of 17–25)
- Moderate (IIEF-EF domain of 11–16)
- Severe (IIEF-EF domain of ≤ 10)

The following analysis set will be used for the statistical analysis of the open-label extension phase:

- The **open-label analysis set** (OLAS) will consist of all subjects who made use of medication at least once during the open-label extension.

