14.5.2 Handling of Missing Values

Full details on the handling of missing values in analyses of all analysis sets, including rules applied to incomplete questionnaires and planned additional analyses, will be defined in the SAP. Only the main principles are given for the analyses on the FAS here.

Summary statistics will present the number of missing values and then will be based on non-missing values.

Any missing values in efficacy questionnaire data that occur during the treatment period and are then followed by observed data shall be treated as missing at random and imputed using a corresponding multiple imputation approach.

All subjects who are withdrawn from the study will be asked to continue with the IIEF and SEP questionnaires if possible. These data will be used as part of the analysis for estimating the treatment effect over 12 weeks, according to the randomised treatment policy.

There can be remaining missing values for the primary endpoints for subjects who leave the study and provide no further questionnaire data. For these subjects, missing values will be handled using a control-based multiple imputation approach. The imputation model for the missing observations in both the MED2005 and placebo (control) groups will be constructed from the control group only (missing not at random [MNAR]). This assumes that efficacy results post withdrawal, for subjects who withdraw, would have mirrored those seen in the placebo group and thus lose any potential MED2005 treatment benefit.

Additional estimands/tests of treatment effect, beyond the primary treatment policy estimand, may be addressed, including exploring other ways of handling missing values, such as fitting repeated measures mixed models.

Summary statistics will present the number of observed values and will then be based on the non-missing values for the open-label extension phase.

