14.5.4 Other Efficacy Variables

All other efficacy variables will be analysed in a supportive way to describe the effect of treatment. Secondary analyses will also be performed on the FAS and with the ANCOVA approach.

Double-blind phase:

The following secondary efficacy analyses will be conducted:

- The analysis of the three co-primary endpoints will be repeated in the three pre-specified subgroups of ED severity: mild, moderate and severe as specified in [Section 14.1](#)
- The change in the IIEF-EF domain, SEP Question 2 and SEP Question 3 at each 4-week visit will be analysed
- Responder analyses assessing the proportion of subjects with a specific increase in the IIEF-EF domain from baseline, using a different responder definition defined separately for each baseline severity group, will be conducted. A responder is defined as having an increase of ≥ 2 , ≥ 5 and ≥ 7 for the mild, moderate and severe subjects, respectively (published Minimal Clinically Important Difference [MCID] according to Rosen *et al.* 2011 [31])
- Responder analyses for SEP Questions 2 and 3 will be conducted in the same way as for the IIEF-EF. A responder is defined as having an increase of -1.3% , 16.7% and 27.3% for SEP Question 2 and 5.0% , 23.3% and 17.0% for SEP Question 3 for patients with mild, moderate and severe baseline ED, respectively (published MCID according to Araujo *et al.* 2012 [32])
- Responder analyses will also be conducted using responder thresholds (that represent meaningful within-patient changes) in the three co-primary endpoints that are determined using a suitable set of data from this study, prior to study unblinding. Receiver operating characteristics (ROC) analyses will be performed to define the thresholds using the PGI-S and PGI-C as anchors, with the thresholds chosen to balance sensitivity and specificity, supplemented with both empirical cumulative distribution functions and probability density functions. The thresholds defined from these analyses will be included in the final SAP prior to breaking the blind.

The following secondary efficacy analyses will be conducted in a more exploratory way making use of the FAS data in the selected doses and placebo over both stages:

- The GAQ will be analysed via logistic regression including terms for treatment group, site and baseline ED severity (categorical variable)

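### Men who stop study drug are asked to continue only the IIEF and SEP, yet PGI-S, PGI-C, GAQ and SEAR are analysed on the FAS as randomised

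*Protocol*

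**What the plan says.** Three places in the protocol set what is collected once a man stops:

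- 9.6.1, stopping study drug: "All subjects who withdraw from the study drug during the double-blind phase will be asked to continue completing the IIEF and SEP questionnaires".
- 9.6.2, leaving the study: "every attempt should be made to continue with the safety and IIEF and SEP questionnaires up to the end of the double-blind phase".
- 14.5.2, missing values: "All subjects who are withdrawn from the study will be asked to continue with the IIEF and SEP questionnaires if possible".

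Sections 9.6.1 and 9.6.2 give the reason, which is to serve the treatment-policy comparison of the primary objective.

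The analysis sections are wider. Section 14.5.4 states: "Secondary analyses will also be performed on the FAS and with the ANCOVA approach". Section 14.1 assigns each man to his randomised arm, "whether or not treatment was discontinued while questionnaire data was collected". Among the exploratory analyses of 14.5.4, "The GAQ will be analysed via logistic regression including terms for treatment group, site and baseline ED severity (categorical variable"); SEAR and PGI-S go into an ANCOVA at Weeks 4, 8 and 12, and PGI-C into an ANOVA. PGI-S and PGI-C have a second use: "Receiver operating characteristics (ROC) analyses will be performed to define the thresholds using the PGI-S and PGI-C as anchors".

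The control-based imputation of 14.5.2 is introduced with "There can be remaining missing values for the primary endpoints for subjects who leave the study and provide no further questionnaire data" and is not extended to other endpoints. The other stated rule, imputation as missing at random, covers gaps that are followed by observed data. Further detail is left to the SAP.

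**The concern.** The collection rule and the analysis rule do not match for four scales. A man who stops stays in the FAS under his randomised arm and is asked for his IIEF and SEP. He is not asked for the short global scales or the SEAR that are scheduled at the same visits. No analysis rule written later can recover an answer that nobody requested, so this part cannot be left to the SAP.

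If few such answers arrive, the results for these scales mainly describe men still using the gel, although they are labelled as FAS results. They would then answer a different question from the primary analysis printed beside them. Unequal stopping between arms is conceivable: 9.6.1 lists intolerable adverse events as a reason to stop, 6.4.2 reports dose-dependent headache with a GTN rectal ointment, and the top dose here is 1.8 mg. Against that, 6.3.3 reports only 15 mild related headaches in 1023 attempts at 0.6 mg.

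**Working it through.** **1. The plan's own figure.** The protocol gives no number on this point. Its only related figure is the 90% power in 14.7, with n = 250 per arm, differences 3.2, 11.5 and 12, SDs 5.6, 33 and 33, and correlations 0.5, 0.5 and 0.6. At two-sided 0.05/3 the critical value is 2.394. The expected z is difference / (SD × √(2/250)):

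- IIEF-EF: 6.39, power 1.000
- SEP Question 2: 3.90, power 0.934
- SEP Question 3: 4.07, power 0.953

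Joint power from the trivariate normal is 0.904, so the 90% is reproduced. It uses only endpoints that are requested after stopping, and the present point does not touch it.

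**2. Collection against analysis.**

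| Instrument | Requested after stopping | Analysed on FAS | Refers to the treatment |
|---|---|---|---|
| IIEF, SEP | yes | yes | no |
| PGI-S | no | yes | no (severity over four weeks, 18.5) |
| SEAR | no | yes | no (18.3) |
| PGI-C | no | yes | yes (change since starting it, 18.5) |
| GAQ | no | yes | yes (18.4) |

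**3. Possible size, continuous scale.** All inputs are assumed. On-drug effect δ = 0.50 SD; effect lost on stopping; stoppers in both arms lie g SD below placebo men still on gel; stoppers' answers unobserved. Let a and p be the stopping proportions in the active and placebo arms.

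As-randomised effect = (1 − a)δ − g(a − p). The observed-only effect is δ.

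| p | a | g | As-randomised effect | Overstatement |
|---|---|---|---|---|
| 5% | 5% | any | 0.95 × 0.50 = 0.475 | 0.025 |
| 10% | 10% | any | 0.90 × 0.50 = 0.450 | 0.050 |
| 20% | 20% | any | 0.80 × 0.50 = 0.400 | 0.100 |
| 5% | 20% | 0.5 | 0.400 − 0.5 × 0.15 = 0.325 | 0.175 |

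**4. Possible direction, yes/no scale.** Also assumed: 50% against 30% answer yes among men still on gel, an observed difference of 20 points. Arm proportion = (1 − stopping) × on-gel rate + stopping × stopper rate.

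- 5% stop in each arm, 10% of stoppers say yes: 48% − 29% = 19 points.
- 10% in each arm, same stoppers: 46% − 28% = 18 points.
- 20% active and 10% placebo, same stoppers: 42% − 28% = 14 points, so 20 overstates by a factor of 20/14 = 1.43.
- 20% active and 10% placebo, but half of active stoppers say yes (they left for an adverse event): 50% − 28% = 22 points, so 20 understates.

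The sign therefore depends on why men stop.

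**5. ROC thresholds.** Simulation with assumed inputs: 1000 men in four arms, IIEF-EF change with SD 5.6 and mean 3 on placebo, 3.2 higher on active, correlation with the anchor about 0.6, and a whole-point cut that balances sensitivity and specificity. The full-data threshold averaged about 6.0 points. Mean shift after dropping stoppers' pairs:

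| Loss | Random | Tied to low anchor | Tied to low IIEF-EF change |
|---|---|---|---|
| 5% | 0.003 | 0.007 | 0.027 |
| 10% | −0.003 | 0.007 | 0.030 |
| 20% | −0.020 | 0.037 | 0.363 |

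**The case against.** The restriction is deliberate and its purpose is stated. The treatment-policy estimand is declared for the primary objective only (7.1); the secondary objectives (7.2) carry none. Section 14.5.4 calls these analyses supportive and puts the four scales in its more exploratory list. FAS names a population and does not by itself commit every scale to one estimand. Sparing withdrawn men extra questionnaires is a fair trade-off. This stands, and it limits the importance of the point. It does not remove the mismatch, because 14.1 describes the efficacy analysis as indifferent to discontinuation and nothing labels these four analyses as on-treatment.

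A reader might infer that the four scales are missing by design. The protocol does not say that they cease: the visit lists in 11.1.3.2 to 11.1.3.4 schedule them beside the IIEF with no on-drug condition. Sparse data is the probable result of a request that names two instruments in three places, but it is an inference. Men who stop late will also have answered at earlier visits.

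GAQ and PGI-C ask about the treatment or the change since starting it, so an answer given weeks after stopping is hard to read. This stands, and it is why the fix treats them differently.

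Missing-data rules may properly wait for the SAP, so the primary-only scope of the control-based imputation is not a fault. What is collected, however, is fixed here.

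**Conclusion.** The point holds as a minor inconsistency with an inexpensive remedy. The protocol analyses PGI-S, PGI-C, GAQ and SEAR as randomised but does not ask for them after stopping, so these data will probably be sparse for men who stop.

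A reader might conclude that the secondary results are biased in favour of the drug. The documents do not support that. Bias relative to the as-randomised comparison arises only if stopping is related to outcome or differs by arm. The protocol gives no stopping rate or pattern, and the illustrations run from an overstatement of 0.175 SD to an understatement of 2 percentage points on assumed inputs alone. At 5% to 10% equal stopping, with the effect lost on stopping, the overstatement is 0.025 to 0.05 SD.

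A reader might also conclude that the anchor-based thresholds are distorted. That is not shown. They are set on a suitable data set before unblinding, and the simulated shift is at most 0.03 IIEF-EF points at 5% to 10% loss. It reaches about 0.4 points only at 20% loss driven by low IIEF-EF change.

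The co-primary endpoints, the success rule and the 90% power are unaffected. So are the other IIEF domains and SEP questions, whose questionnaires are requested after stopping.

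**What to change.** In 9.6.1, 9.6.2 and 14.5.2, extend the request so that men who stop study drug also complete PGI-S, and SEAR if willing, at the scheduled visits where the IIEF is already requested. State that these data are analysed as randomised.

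For PGI-C and GAQ, choose one of two courses. Either add them to the request with a sentence on how an answer given after stopping is to be interpreted, or state in 14.5.4 that these two analyses describe on-treatment responses.

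The cost is one amended sentence in three places, a clarifying sentence in 14.5.4, and a few minutes of extra burden for withdrawn men at visits already requested. It needs doing while men are still in the treatment period, since the answers cannot be collected afterwards.

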9.6.2 Criteria for Withdrawal from the Study

Subjects (and their female partners) are free to withdraw from the study at any time, without prejudice (withdrawal of consent).

Subjects may be withdrawn from the study at any time; however, once treatment has commenced, every attempt should be made to continue with the safety and IIEF and SEP questionnaires up to the end of the double-blind phase to ensure the safety of the subject and in order to address the primary efficacy objective of difference between treatment policies.

Reasons for withdrawing a subject from the study can include:

- Voluntary discontinuation by the subject and/or his female partner, who are free to discontinue participation in the study at any time
- Severe non-compliance to the protocol as judged by the PI and/or Sponsor
- Any other reason as judged by the PI

9.6.3 Procedures for Subject Withdrawal

Subjects who withdraw from the study (and their female partners) should always be asked about their reason(s) for withdrawal and the presence of any AEs. Study-related AEs will be monitored closely and provided with the appropriate medical care and follow-up.

10. STUDY AND CONCOMITANT TREATMENTS

10.1 Investigational Medicinal Product

The IMP under study is MED2005, a gel formulation of GTN currently under development by FMD as a topical treatment for ED. The matching placebo used will be the vehicle gel containing no active ingredients.

During the double-blind phase, MED2005 (at three strengths: 0.2% GTN gel, 0.4% GTN gel and 0.6% GTN gel) or placebo (vehicle gel) will be provided in single unit dose aluminium tubes with 800 mg of gel in every tube packed in cartoon boxes of 4 tubes per box. For each subject, 12 units will be supplied for each of the three 4-week periods during treatment (Weeks 1–4, 5–8 and 9–12).

During the open-label extension phase, MED2005 0.6% GTN gel will be provided in single unit dose aluminium tubes with 800 mg of gel in every tube packed in cartoon boxes of 4 tubes per box. For each 3-month period of the extension phase, 12 units per month (36 tubes at each visit [Visits 6, 7, 8 and 9]) will be supplied to each subject to allow them to use the tubes as they require.

Each 800 mg filled tube will contain sufficient gel to apply a single dose (approximately 300 mg) of MED2005 (0.2%, 0.4% or 0.6%) or placebo at each application. Subjects and their female partners will be trained on the application of the gel to the glans of the penis and cautioned not to use more than one tube of gel per sexual intercourse event. Subjects will be asked to leave a washout period of at least 12 hours before the next attempt at sexual intercourse using the IMP. The placebo gel will be identical in appearance to the three active MED2005 gels and will be administered in the same way and at the same volume as MED2005.

The IMP will be clearly labelled with text that is in full regulatory compliance with each participating country and is translated into the required language(s) for each of those countries.

10.2 Methods of Assigning Subjects to Treatment Groups

See [Section 9.5](#) above for details of randomisation.

10.3 Drug Accountability

The PI, trained delegate or pharmacy staff (as applicable) is responsible for the correct storage of the study medication according to the manufacturer's recommendations. The medication made available for this clinical study must be used in accordance with the protocol and must only be handled by the pharmacist or other authorised personnel. The pharmacy staff must maintain complete and accurate records, showing the receipt and disposition of all supplies of the study medication. These records must include a master record which lists the date of receipt of all study medication and the quantities received, and a dispensing record which includes all quantities dispensed, the subject numbers to whom the medication was dispensed, the date of each dispensing and the identification of the dispenser. IMP will not be destroyed without prior written confirmation from the Sponsor. The Clinical Research Organisation (CRO) will be responsible for coordinating the destruction of any unused medication at the sites.

Written proof of destruction must be kept in the Sponsor Oversight File and/or the Trial Master File (TMF) and Investigator Site File.

At site visits at the end of each of the three 4-week periods during treatment in the double-blind phase (i.e. at Visits 3, 4 and 5) and at the end of each of the 3-month periods during the open-label extension phase (i.e. at Visits 7, 8, 9 and 10), subjects will be asked to return used and unused tubes of IMP to enable the clinical staff to check treatment compliance. Clinical staff will examine the IMP tubes visually to check if the tube has been pierced to help assess subject compliance and allow re-training on expressing a dose if deemed necessary.

